6.3.2. PD Endpoints

None.

6.4. Covariates

None.

7. HANDLING OF MISSING VALUES

For the analysis of safety endpoints, the sponsor data standard rules for imputation will be applied.

7.1. Concentrations Below the Limit of Quantification

In all data presentations (except listings), concentrations below the limit of quantification (BLQ) will be set to zero. (In listings BLQ values will be reported as “<LLQ”, where LLQ will be replaced with the value for the lower limit of quantification.)

7.2. Deviations, Missing Concentrations and Anomalous Values

In summary tables and plots of median profiles, statistics will be calculated having set concentrations to missing if 1 of the following cases is true:

1. A concentration has been collected as ND (ie, not done) or NS (ie, no sample),
2. A deviation in sampling time is of sufficient concern or a concentration has been flagged anomalous by the pharmacokineticist.

Note that summary statistics will not be presented at a particular time point if more than 50% of the data are missing.

7.3. Pharmacokinetic Parameters

Actual PK sampling times will be used in the derivation of PK parameters.

If a PK parameter cannot be derived from a subject's concentration data, the parameter will be coded as NC (ie, not calculated). (Note that NC values will not be generated beyond the day that a subject discontinues).

In summary tables, statistics will be calculated by setting NC values to missing; and statistics will be presented for a particular treatment with ≥ 3 evaluable measurements. For statistical analyses (ie, analysis of variance), PK parameters coded as NC will also be set to missing; and analyses will not be performed for a particular parameter if more than 50% of the data are NC.

If an individual subject has a known biased estimate of a PK parameter (due for example to an unexpected event such as vomiting before all the compound is adequately absorbed in the body), this will be footnoted in summary tables and will not be included in the calculation of summary statistics or statistical analyses.

8. STATISTICAL METHODOLOGY AND STATISTICAL ANALYSES

8.1. Statistical Methods

The interactive effect on PK parameters will be determined by constructing 90% confidence intervals around the estimated difference between the Test and Reference treatments using a mixed effects model based on natural log transformed data. The mixed effects model will be implemented using SAS Proc Mixed, with REML estimation method and Kenward-Roger degrees of freedom algorithm.

8.2. Statistical Analyses

Actual PK sampling times will be used in the derivation of PK parameters.

Natural log transformed AUC_{inf}, AUC_{last}, C_{max} and C_{LR} of metformin will be analyzed using a mixed effect model with sequence, period and treatment as fixed effects and participant within sequence as a random effect.

Additionally, AUC₂₄, C_{max} and C_{LR} of NMN will also be analyzed using a mixed effect model with sequence, period and treatment as fixed effects and participant within sequence as a random effect. Estimates of the adjusted mean differences (Test-Reference) and corresponding 90% confidence intervals will be obtained from the model. The adjusted mean differences and 90% confidence intervals for the differences will be exponentiated to provide estimates of the ratio of adjusted geometric means (Test/Reference) and 90% confidence intervals for the ratios. Metformin alone will be the Reference treatment, while the metformin co-administered with PF-04965842 will be the Test treatment.

PK parameters will be summarized descriptively by analyte and by treatment, as applicable, in accordance with Pfizer Data Standards. Concentrations will be listed and summarized descriptively by analyte, nominal PK sampling time and treatment. Individual subject and median profiles of the plasma concentration-time data will be plotted by treatment using actual and nominal times, respectively. Median profiles will be presented on both linear-linear and log-linear scales.

Individual changes from baseline for metformin CLR versus NMN CLR will be plotted and a Pearson correlation coefficient (r) will be presented.

Residuals from the model will be examined for normality and the presence of outliers via visual inspection of plots of residuals vs predicted values and normal probability plots of residuals but these will not be included in the clinical study report. If there are major deviations from normality or outliers then the effect of these on the conclusions will be investigated through alternative transformations and/or analyses excluding outliers. Justification for any alternative to the planned analysis will be given in the report of the study.

Table 3. PK Parameters to be Summarized Descriptively by Treatment

Parameter	Summary Statistics
AUC _{inf} , AUC _{last} , AUC ₂₄ , C _{max} , CL/F, CL _r , V/F	N, arithmetic mean, median, cv%, standard deviation, minimum, maximum, geometric mean and geometric cv%.
T _{max}	N, median, minimum, maximum.
t _{1/2} , AE, Ae%	N, arithmetic mean, median, cv%, standard deviation, minimum, maximum.

Supporting data from the estimation of t_{1/2} and AUC_{inf} will be listed by treatment and analyte: terminal phase rate constant (kel); goodness of fit statistic from the log-linear regression (r²); the percent of AUC_{inf} based on extrapolation (AUC_{extrap} %); and the first, last, and number of time points used in the estimation of kel. This data may be included in the clinical study report.

Presentations for metformin and NMN concentrations will include:

- A listing of all concentrations sorted by analyte, subject ID, period and nominal time postdose. The concentration listing will also include the actual times. Deviations from the nominal time will be given in a separate listing.
- A summary of concentrations (for each analyte) by treatment and nominal time postdose, where the set of statistics will include n, mean, median, standard deviation, coefficient of variation (cv), minimum, maximum and the number of concentrations above the lower limit of quantification.

- Median concentrations time plots (on both linear and semi-log scales for each analyte) against nominal time postdose by treatment (all treatments on the same plot per scale, based on the summary of concentrations by treatment and time postdose).
- Mean concentrations time plots (on both linear and semi-log scales for each analyte) against nominal time postdose by treatment (all treatments on the same plot per scale, based on the summary of concentrations by treatment and time postdose).
- Individual concentration time plots by treatment (on both linear and semi-log scales for each analyte) against actual time postdose (there will be separate spaghetti plots for each treatment per scale).
- Individual concentration time plots by subject (on both linear and semi-log scales for each analyte) against actual time postdose [there will be separate plots for each subject (containing all treatments) per scale].
- Individual changes from baseline for metformin CL_r versus NMN CL_r will be evaluated using a regression line and Pearson correlation coefficient (r).

For summary statistics, median and mean plots by sampling time, the nominal PK sampling time will be used, for individual subject plots by time, the actual PK sampling time will be used.

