9.2. Sample Size Determination

A sample size of 12 participants will provide 90% confidence intervals for the difference between treatments of ± 0.134 , ± 0.161 and ± 0.148 on the natural log scale for metformin AUC_{inf}, C_{max} and CL_r, respectively, with 80% coverage probability. The following table presents the width of 90% confidence interval for different estimated effects (Table 4):

Parameter	Estimated Effect (100*Test/Reference)	90% CI	CI Width
CLr	60%	51.73, 69.60	17.88
	70%	60.35, 81.20	20.85
	80%	68.97, 92.80	23.83
	90%	77.59, 104.40	26.81

Table 4.	Sample Size Determination
----------	---------------------------

	100%	86.21, 115.99	29.79
AUCinf	100%	87.47, 114.32	26.84
	120%	104.97, 137.18	32.22
	160%	139.96, 182.91	42.95
	200%	174.94, 228.63	53.69
Cmax	100%	85.10, 117.50	32.39
	120%	102.13, 141.00	38.88
	160%	136.17, 188.00	51.83
	200%	170.21, 235.00	64.79

Abbreviation: CI = confidence interval

These calculations are based on estimates of within participant standard deviations of 0.156, 0.188 and 0.173 for log_e AUC_{inf}, log_e C_{max} and log_e CL_r of metformin, respectively, as obtained from internal and/or external data in previous clinical studies with metformin.^{10, 11}

Participants who discontinued from the study may be replaced at the sponsor's discretion.

Population	Description
Enrolled	All participants who sign the ICD.
Randomly assigned to investigational product	Participants will be randomized to 1 of 2 treatment sequences in a 2-way crossover design. A total of 12 healthy participants will be enrolled in the study so that 6 participants will be enrolled in each treatment sequence.
PK Population	The pharmacokinetic (PK) concentration population is defined as all enrolled subjects who received at least 1 dose of metformin and in whom at least 1 plasma concentration value is reported.
Safety Population	All participants randomly assigned to investigational product and who take at least 1 dose of investigational product. Participants will be analyzed according to the product they actually received.

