PK parameters in Table 6 will be summarized descriptively by analyte and by treatment, as applicable, in accordance with Pfizer Data Standards. Concentrations will be listed and summarized descriptively by analyte, nominal PK sampling time and treatment. Individual subject and median profiles of the plasma concentration-time data will be plotted by treatment using actual and nominal times, respectively. Median profiles will be presented on both linear-linear and log-linear scales. Individual changes from baseline for metformin CL_r versus NMN CL_r will be plotted and a Pearson correlation coefficient (r) will be presented.

Natural log transformed AUC_{inf}, AUC_{last}, C_{max} and CL_r of metformin will be analyzed using a mixed effect model with sequence, period and treatment as fixed effects and participant within sequence as a random effect. Additionally, AUC₂₄, C_{max} and CL_r of NMN will also be analyzed using a mixed effect model with sequence, period and treatment as fixed effects and participant within sequence as a random effect. Estimates of the adjusted mean differences (Test-Reference) and corresponding 90% confidence intervals will be obtained from the model. The adjusted mean differences and 90% confidence intervals for the differences will be exponentiated to provide estimates of the ratio of adjusted geometric means (Test/Reference) and 90% confidence intervals for the ratios. Metformin alone will be the Reference treatment, while the metformin co-administered with PF-04965842 will be the Test treatment.

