2.2. Study Objectives

Primary Objective

- *To estimate the effect of PF-04965842 on MATE1/2K activity via the pharmacokinetic assessment of a single, oral dose of metformin in healthy participants.*

Secondary Objective

- *To evaluate the PK, safety and tolerability of a single oral dose of metformin when co-administered with PF-04965842.*

Exploratory/Tertiary Objectives

- *To evaluate the effects of PF-04965842 on N^l-methylnicotinamide.*
- *To correlate the effects of PF-04965842 on N^l-methylnicotinamide versus metformin.*
- *To enable exploratory research through the collection of banked biospecimens, unless prohibited by local regulations or ethics committee decision.*

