4.2. Statistical Decision Rules

There are no statistical decision rules.

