6.3. Other Endpoints

6.3.1. PK Endpoints

PK analysis of metformin and NMN (N1-methylnicotinamide) will be taken according to the Schedule of Activities given in the protocol.

The following PK parameters will be calculated by treatment and by analyte (if applicable) from the concentration-time data and urine concentrations using standard noncompartmental methods:

Table 2. Noncompartmental PK Parameters

PK Parameter	Analysis Scale	Metformin	NMN (N1-methylnicotinamide)
AUC _{inf} [*]	ln	A, D	
AUC _{last}	ln	A, D	D
AUC ₂₄	ln	D	A, D
C _{max}	ln	A, D	A, D
T _{max}	R	D	D
t _{1/2} [*]	R	D	
CL/F [*]	ln	D	
V/F*	ln	D	
Ae [*]	R	D	D
Ae% [*]	R	D	
CL _r [*]	ln	A, D	A, D

Key: A=analyzed using statistical model, D=displayed with descriptive statistics, ln=natural-log transformed, R=raw (untransformed), *=if data permits

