10. APPENDICES

Appendix 1. SAS CODE FOR ANALYSES

- Analyze AUC_{inf}, AUC_{last}, C_{max} and CL_r of metformin.
- Analyze AUC₂₄, C_{max} and CL_r of NMN.

An example of the PROC MIXED code is provided below:

```
proc mixed data=tab.pk;
  class seq period trt subject;
  model l&var=seq period trt/ ddfm=KR;
  random subject(seq) /subject=subject(seq);
  lsmeans trt;
  estimate 'Test vs Reference' trt -1 1 /cl alpha=0.1;
  ods 'Estimates' out=est&var;
  ods 'lsmeans' out=ls&var;
  ods 'covparms' out=cov&var;
  ods 'tests3' out=tst&var;
run;
/* Letter assignments for treatments (trt) within the estimate statement above are as follows;
```

A = metformin alone (Reference);

B = metformin co-administered with PF-04965842 (Test) */;

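### The exploratory metformin–NMN CLr correlation pools both sequences with no period adjustment, although the mixed model for the same endpoints has one; adjusting for sequence is a cheap improvement.

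*SAP*

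**What the plan says.** One exploratory objective (SAP 2.2) begins "To correlate the effects of PF-04965842 on" and goes on to name NMN versus metformin. Its planned analysis appears in three places. In SAP 8.2, "Individual changes from baseline for metformin CLR versus NMN CLR will be plotted and a Pearson correlation coefficient (r) will be presented". Later in the same section, the list of presentations says that these changes "will be evaluated using a regression line and Pearson correlation coefficient (r". Protocol 9.4.4.2 says that they "will be plotted and a Pearson correlation coefficient (r) will be presented". None of the three mentions period or sequence, states the scale, or says what baseline means for CLr.

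For the same CLr data, SAP 8.2 specifies a mixed model with sequence, period and treatment as fixed effects. The code in SAP Appendix 1 matches: "model l&var=seq period trt/ ddfm=KR". SAP Table 2 assigns CLr of both analytes the log scale under its key "ln=natural-log transformed, R=raw (untransformed". On the use of results, SAP 4.2 says "There are no statistical decision rules".

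**The concern.** The plan allows for period when it estimates the mean effect on CLr, but not when it correlates the individual effects. The pooled scatter mixes two groups whose B−A changes carry the period effect with opposite signs. If both analytes have a period effect, the two groups separate along both axes, and that separation enters r and the slope. With no true association, r is pushed up when the two effects have the same sign and down when they are opposite. With a true association, a period effect in one analyte alone weakens r.

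At stake is the reading of r and the regression line, the planned summary of how well NMN tracks metformin as a marker of MATE activity. Part of r could reflect the period and not PF-04965842.

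**Working it through.** **Inputs from the documents.** Twelve participants, 6 per sequence (Protocol 4.1, SAP 2.1). Protocol 9.2 gives "estimates of within participant standard deviations of 0.156, 0.188 and 0.173" for log AUCinf, log Cmax and log CLr of metformin, so the CLr value is 0.173. CLr is Ae/AUC (Protocol Table 6).

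**Assumed, not in the documents.** The period effect π (period 2 minus period 1, ln scale), tried at 0.05, 0.10 and 0.20. The NMN within-participant SD, tried at 0.15, 0.173 and 0.25.

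**Check of the SD against the plan's own figure.** Half-width of the 90% CI = t(0.95; 10 df) × SD × √(2/12) × √(χ²(0.80; 10 df)/10) = 1.8125 × 0.173 × 0.4082 × √1.3442 = 0.148. This is the ±0.148 stated for CLr. The same formula gives the stated ±0.134 and ±0.161 for AUCinf and Cmax. The documents state no figure for the correlation.

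**Which change can be computed.** The SAP defines baseline only for safety data, as a predose value in each period (6.2.2 to 6.2.4). Protocol Table 2 has only a spot blank before dosing, and all timed urine is postdose. No predose CLr therefore exists for either analyte, and the only within-participant change available is Treatment B against Treatment A.

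**Mechanism.** Let d = ln CLr(B) − ln CLr(A). Its mean is τ + π in Sequence 1 and τ − π in Sequence 2. With equal sequences, the population r over all participants is

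(c + πM·πN) / √[(VM + πM²)(VN + πN²)],

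where V = 2·SD² and c is the within-sequence covariance. In a sample of 12, π² is multiplied by 12/11. For equal SDs of 0.173, equal π and c = 0, the plug-in value is (12/11)π² / (2 × 0.173² + (12/11)π²):

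- π = 0.05: 0.00273/(0.05986 + 0.00273) = 0.044
- π = 0.10: 0.01091/(0.05986 + 0.01091) = 0.154
- π = 0.20: 0.04364/(0.05986 + 0.04364) = 0.422

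**Simulation.** 200,000 trials per case, with no between-participant variation in drug effect, no true association and the same π in both analytes. Ranges are over the NMN SDs. The flag column is the chance that at least one of the two models' period tests reaches 5%.

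| π (ln) | mean r | slope, NMN on metformin (true 0) | at least one period test flags |
|---|---|---|---|
| 0.05 | 0.03–0.05 | 0.04 | – |
| 0.10 | 0.11–0.17 | 0.16 | 36–49% |
| 0.20 | 0.33–0.46 | 0.44 | 84–96% |

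Opposite signs give the same sizes of r, negative. With no period effect, r has an SD of 0.30 and a 5th–95th percentile range of −0.50 to 0.50.

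With a true correlation of 0.5 (mean r 0.48 without a period effect):

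- same-sign 0.10 gives 0.54–0.57
- opposite-sign 0.10 gives 0.22–0.31
- 0.20 in one analyte only gives 0.34–0.41

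**Sensitivity.** If the drug effect itself varies between participants with an assumed SD of 0.15 ln in each analyte, uncorrelated, and NMN SD is 0.173, mean r falls to about 0.11 at π = 0.10 and about 0.34 at π = 0.20.

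**After centring within sequence.** Mean r returns to 0.00 or 0.48 in every simulated case.

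**The case against.** The strongest reply is that the distortion is hypothetical. No period effect is documented, and the design works against one: a single confinement with dosing days at least 4 days apart, standardised meals and dosing times, one metformin lot, and normal creatinine clearance at entry. The largest figures need a 0.20 ln shift (e^0.20 = 1.22, about 22%) in both analytes, which exceeds the within-participant SD of 0.173. Leaving out variation in drug effect also overstates r. All of this stands, and it is why the figures above are upper-end.

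A second reply is that the mixed models would show a period effect. At 0.20 that is largely right: one or other test flags in 84–96% of trials. At 0.10 it is only 36–49%, so a clean pair of period tests is weak reassurance there. Using two tests also raises the false-alarm rate to about 10%.

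Third, NMN and metformin are measured in aliquots of the same urine collection (Protocol Table 2, footnote b), so a lost void shifts both CLr values together. With an assumed shared error of 0.08 ln inside the 0.173, the population r is 0.08²/0.173² = 0.0064/0.0299 = 0.21 with no drug-related association, and centring does not change it. This is a separate source of correlation. It limits what an adjusted r can claim but does not argue against adjusting for period.

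Last, a plain Pearson r is a legitimate descriptive choice for an exploratory aim. Keeping it as a supportive figure meets that point.

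**Conclusion.** The concern holds as a low-severity improvement. The missing period term is plain from the text, and the direction of its effect follows from algebra. The size rests on assumed period effects and an assumed NMN SD: negligible at 0.05 ln, modest beside chance variation at 0.10, and material only at about 0.20 in both analytes.

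A reader might infer three stronger things that the documents do not support:

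- **That the planned r will be biased.** No period effect is reported, and without one there is no distortion.
- **That the main result is at risk.** The mixed model for metformin CLr includes period and is untouched, and no hypothesis or decision rule depends on r.
- **That the undefined baseline is a separate error.** Only B versus A can be computed, Test minus Reference is the contrast used elsewhere in SAP 8.2, and Table 2 already puts CLr on the log scale. Stating contrast and scale is a clarification that comes with the fix.

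**What to change.** In both places in SAP 8.2, state: *For each participant with both periods evaluable, change = ln CLr(Treatment B) − ln CLr(Treatment A) for each analyte. Pearson r and the regression line will be computed after subtracting the sequence mean change; the unadjusted r will be given as supportive, with points marked by sequence.* Align Protocol 9.4.4.2. Leave the mixed models as they are.

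The change needs no new samples or parameters. It costs one degree of freedom: the SD of r under no association rises from 0.30 to 0.32. The Fisher 95% CI for an observed r of 0.5, tanh(0.549 ± 1.96/√(n − 3)), goes from −0.10 to 0.83 (n = 12) to −0.14 to 0.85 (n taken as 11). If there is no period effect, that small loss buys nothing. The report should also say that the adjusted r removes the period contribution only, not correlation from errors in the shared urine collection.

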Preclinical in vitro inhibition studies showed that the unbound maximum observed concentration $(C_{max})/50\%$ inhibitory concentration (IC50) ratio is 0.24 and 0.13 for multidrug and toxic compound extrusion transporter (MATE)1 and MATE2K, respectively, suggesting that PF-04965842 has a potential to inhibit these drug transporters in vivo as ratios exceed the in vitro regulatory threshold unbound C_{max}/IC_{50} ratio of 0.02.⁸ Therefore, a clinical interaction study with a sensitive MATE1 and MATE2K substrate is needed to assess the effect of PF-04965842 on the activity of these transporters. The primary purpose of this study is to assess the effect of PF-04965842 on the in vivo pharmacokinetics (PK) of metformin, a sensitive substrate for MATE1 and MATE2K.⁸ Metformin is also a substrate for organic cation transporter (OCT)1 and OCT2. However, PF-04965842 is not an inhibitor of OCT2 (C_{max}/IC50 ratio is >300) and despite the unbound PF-04965842 C_{max}/IC50 ratio for OCT1 being just above 0.02 (0.03), inhibition of OCT1, a hepatic uptake transporter, is not expected to increase plasma metformin exposures as OCT1 does not modulate metformin clearance as it is primarily excreted unchanged in urine. Both MATE1 and MATE2K are renal transporters that are expressed in the apical membrane of the renal proximal tubules thus play an important role in tubular secretion and reabsorption of drug molecules in the kidney. Therefore, significant MATE1/2K inhibition would primarily impact the renal clearance of substrates for these transporters with having minimal effects, if any, on plasma exposures.

 N^{1} -methylnicotinamide (NMN), a metabolite of niacin, has been reported to be an endogenous biomarker for assessing MATE/OCT2 inhibition. Renal clearance of NMN was shown to be reduced by ~70% by pyrimethamine, a potent MATE/OCT2 inhibitor.⁹ As such, NMN is being assessed in this study to further investigate the utility of this endogenous substance as a biomarker for MATE activity in comparison to metformin, the gold standard for assessing MATE activity in drug-drug interaction (DDI) studies.⁸

Objectives and Endpoints

Objectives:	Endpoints:
Primary:	Primary:
• To estimate the effect of PF-04965842 on MATE1/2K activity via the pharmacokinetic assessment of a single, oral dose of metformin in healthy participants.	Metformin CL _{r.}
Secondary:	Secondary:

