Preliminary SimCYP[®] modelling of PF-04965842 dosed at 200 mg QD indicated a low risk of precipitating a significant drug interaction with metformin, a MATE1 and MATE2K substrate. Additionally, PF-04965842 did not significantly affect 24 hour urinary creatinine (a MATE1/2K and OCT2 substrate) up to doses of 800 mg in clinical studies.

Banked biospecimens will be collected for exploratory

pharmacogenomic/genomic/biomarker analyses and retained in the Biospecimen Banking System (BBS), which makes it possible to better understand the investigational product's mechanism of action and to seek explanations for differences in, for example, exposure, tolerability, safety, and/or efficacy not anticipated prior to the beginning of the study.

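### No formal contrast of the NMN and metformin CLr effects is planned, and Pearson r at one regimen does not measure agreement in effect size

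*SAP*

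**What the plan says.** The exploratory objective in SAP 2.2 is "To correlate the effects of PF-04965842 on N^l-methylnicotinamide versus metformin". The Protocol Synopsis gives the wider purpose of measuring NMN: "to further investigate the utility of this endogenous substance as a biomarker for MATE activity in comparison to metformin".

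SAP 8.2 plans two kinds of analysis that bear on this.

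- **Separate models.** Metformin CLr is modelled on the log scale, and CLr "of NMN will also be analyzed using a mixed effect model with sequence, period and treatment as fixed effects". Each difference is "exponentiated to provide estimates of the ratio of adjusted geometric means (Test/Reference) and 90% confidence intervals for the ratios". The example code in SAP Appendix 1 takes one variable at a time.
- **Joint display.** "Individual changes from baseline for metformin CLR versus NMN CLR will be plotted and a Pearson correlation coefficient (r) will be presented". The list of presentations later in 8.2 says that the same changes "will be evaluated using a regression line and Pearson correlation coefficient (r)". Protocol 9.4.4.2 has the plot and r but not the line.

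No CI for r, no contrast between the two ratios and no guidance on reading r is given. SAP 6.2 defines baseline for laboratory, vital-sign and ECG data, but the SAP does not define it for CLr. It also does not say whether the change is raw or logarithmic.

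**The concern.** A biomarker is useful here if it shows roughly the same inhibition as metformin. Pearson r is unchanged by shift and scale: if NMN showed half the metformin log effect in everyone, r would not register it. With a single regimen there is no dose range to spread the effects out. What r picks up is how much the true effect varies between people relative to within-person noise, plus any error common to both assays. The protocol expects little inhibition: in Protocol 4.2, preliminary modelling "indicated a low risk of precipitating a significant drug interaction with metformin". A small effect leaves little room for true variation between people.

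The two separate 90% CIs do not fill the gap. Both analytes come from the same participants and periods, so the interval for the ratio of the two effects cannot be read off the separate intervals. What is at stake is how the NMN result is interpreted. The primary endpoint is not affected.

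**Working it through.** **Inputs from the documents.** N = 12 in a 2×2 crossover; within-participant SD of log metformin CLr sM = 0.173; stated 90% CI half-width ±0.148 with 80% coverage probability (Protocol 9.2). One regimen, 200 mg once daily for 2 days. The same urine containers and volumes supply one aliquot per analyte (Protocol Table 2, footnote b), for NMN over 0–24 h and for metformin over 0–48 h.

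**Assumed, because the documents do not give them.** NMN SD sN = 0.173 (range 0.10 to 0.25); correlation ρ of same-period errors 0 to 0.8; between-person SD τ of the true log effect 0 to 0.20; a perfect biomarker, meaning the same true log effect on both analytes in each person.

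**1. The protocol's figure.** Half-width = t(0.95, 10) × s × √(2/12) × √(χ²(0.80, 10)/10) = 1.812 × 0.173 × 0.408 × 1.159 = 0.148. The same formula gives 0.134 for AUCinf and 0.161 for Cmax, as stated.

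**2. Pearson r on log changes.** The population value is

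r = (τ² + 2ρ·sM·sN) / √[(τ² + 2sM²)(τ² + 2sN²)].

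With τ = 0.10, ρ = 0 and both SDs 0.173: 0.0100 / (0.0100 + 0.0599) = 0.14. Simulating 100,000 trials of n = 12 gives:

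| τ | ρ | mean r | 5th to 95th percentile |
|---|---|---|---|
| 0 | 0 | 0.00 | −0.50 to 0.50 |
| 0.05 | 0 | 0.04 | −0.46 to 0.53 |
| 0.10 | 0 | 0.14 | −0.37 to 0.60 |
| 0.20 | 0 | 0.39 | −0.10 to 0.76 |
| 0 | 0.3 | 0.29 | −0.22 to 0.70 |
| 0 | 0.5 | 0.48 | 0.03 to 0.81 |
| 0 | 0.8 | 0.79 | 0.54 to 0.93 |

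The mean effect does not enter the formula, so the last three rows apply equally when there is no inhibition at all. At τ = 0.10 and ρ = 0, r is zero or negative in 32% of trials. The slope of the NMN change on the metformin change has median 0.14 instead of 1, because noise in the metformin change flattens it.

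**3. Scale.** Suppose both clearances fall to 30% of reference in everyone, with a between-person SD of 0.25 and a correlation of 0.7 between the two underlying clearances (both assumed). Mean r is then 0.00 on log changes and 0.32 on raw changes. The undefined scale therefore matters.

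**4. Direct contrast.** Take D = ln(NMN CLr / metformin CLr) per participant and period. Its within-participant SD is sD = √(sM² + sN² − 2ρ·sM·sN), and a shared individual effect cancels. Putting sD into the step 1 formula gives the log-scale half-width at 80% assurance:

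| sN | ρ = 0 | ρ = 0.5 |
|---|---|---|
| 0.10 | 0.171 | 0.129 |
| 0.173 | 0.210 | 0.148 |
| 0.25 | 0.261 | 0.190 |

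For sN = 0.173 and ρ = 0, sD = 0.245. The limits are the estimate × 0.81 to × 1.23, and the average half-width is about ±0.177.

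**The case against.** The stated objective is only to correlate, it is exploratory, and the SAP has no hypotheses or decision rules. A plot, r and a line address that wording. The two CLr ratios will stand side by side on one scale, so a marked difference in size would be visible. All of this stands, and it limits the point to an improvement.

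A reader might infer three stronger things that the documents do not support.

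- **That the biomarker objective cannot be answered.** The literal objective can be; it is the wider purpose in the Synopsis and Protocol 4.2 that is poorly served.
- **That r must sit near zero for a perfect biomarker.** This needs independent errors and a nearly uniform effect. The documents give neither ρ nor τ, and the shared urine makes a positive ρ possible.
- **That a low r would be reported as failure of NMN.** No text says so; the gap is that no reading is stated in advance.

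The direct contrast also has limits. If metformin CLr falls 20% and NMN shows half that log effect, its 90% CI excludes 1 only about 28% of the time, and about 51% for a 30% fall (both SDs 0.173, ρ = 0). If neither clearance changes, a ratio near 1 says nothing about NMN.

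**Conclusion.** The point holds as a cheap improvement to an exploratory analysis. No formal contrast of the two CLr effects is planned, and the joint analyses do not measure agreement in effect size. Under the stated assumptions, mean r runs from 0.00 to 0.39 for a perfect biomarker with independent errors. It reaches 0.29 to 0.79 from correlated error alone. So r is uninformative in both directions, rather than biased in a known one. These figures rest on the protocol's SD of 0.173 for metformin and on assumed values for the NMN SD, ρ and τ. That no contrast is planned, and that r ignores shift and scale, needs none of these assumptions.

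**What to change.** In SAP 8.2 and Protocol 9.4.4.2:

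- **Add a contrast.** Fit the planned PROC MIXED model to ln(NMN CLr / metformin CLr) per participant and period. Report the NMN Test/Reference ratio divided by the metformin ratio, with a 90% CI. With complete data this is equivalent to a joint model that lets same-period errors and individual treatment effects correlate across analytes. A joint model with only participant and participant-by-analyte random effects would not do: shared variation in effect would enter its residual. At τ = 0.20 and ρ = 0 its half-width would be about t(0.95, 20) × √[2(0.173² + 0.20²/2)] × √(1/6) = 1.725 × 0.316 × 0.408 = 0.223, against 1.812 × 0.245 × 0.408 = 0.181 for the log-ratio model (neither includes the 80% assurance factor).
- **Keep the plot and r as descriptive.** Define the change as log(Treatment B / Treatment A) and give a CI for r.
- **State the reading in advance.** r alone, high or low, neither establishes nor refutes NMN as a biomarker. A ratio of ratios near 1 is not validation if neither clearance changes.

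The cost is one extra model on data already collected and a few lines of text. The downside is limited precision if the effect is small.
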